Analysis plan:

Data Analysis: Analyses will be performed using SPSS version 22 to run diagnostics (tests for normality, multicollinearity, heteroscedasticity) to assess violations of analytic assumptions, univariate statistics, bivariate tests, and multivariate linear regression. Because study retention may be influenced by preconditions, t-tests or Wilcoxon test will be used to compare intervention group and control group on all T1 variables. T- tests can be used for normal distribution while Wilcoxon test can be used in skewed distribution. Implications of significant differences will be discussed. Based on the intent to treat approach, missing T2 data will be imputed to retain all participants in analyses. We will include all participants who provide informed consent and engage in the T1 assessment, regardless of what portion of the assigned treatment or control protocol is completed. Data will be imputed using multiple imputation for participants who fail to complete the T2 (posttest) assessment.

Sensitivity analyses will explore the implications of the imputation methods employed (e.g., multiple imputation, propensity score matching). Post- recruitment attrition (loss of potential participants who were recruited but failed to engage in any assessments or part of the treatment or control protocol) will be explored in all discussion and implications of study findings. The following series of regressions will assess study hypotheses.

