Hypothesis 1: Exposure to mhealth intervention will result in significant improvement in PrEP adherence compared to the control group. We will firstly examine the distribution of all variables and their correlations. Where two similar variables are correlated at $r>0.4$, 1 variable will be selected for inclusion in regression models to avoid collinearity (see Patel et al., 2016). We will employ multivariate linear regression to estimate the association between the intervention and PrEP adherence. In order to compare the difference of PrEP adherence (after 12 weeks) between intervention group and control group, the first regression model will only include the dichotomous treatment variable (intervention group versus control). Based on the first model, the second regression model will add three confounders (three demographic variables: age, education, and income) to compare the gaps after controlling for age, education and income level. Based on the second model, besides the 3 confounders, the third regression model will add an interaction term, the dichotomous treatment variable and the dichotomous intervention variable (before the intervention vs after) and their interaction. The coefficient of the interaction term will be the difference between the increase in intervention group and the increase in control group.

Hypothesis 2: The impact of intervention on the primary outcome will be mediated through key factors, i.e. increased PrEP self-efficacy, increased PrEP knowledge, increased intention to follow PrEP guidelines, and reduced stress burden. To test

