Measures. Both baseline (T1) and 12-week follow up (T2) data will be collected on the following key measures: **Primary outcome measure:** The primary outcome compares differences between (T1) and (T2) for the key measure of interest: PrEP adherence: Our Phase 1 open-ended data revealed participants' general discomfort with blood tests and needles. Thus, we will not seek PrEP blood levels in Phase 2 to measure adherence as doing so would likely pose a barrier to recruitment and retention. Instead, we will use Wilson's simple 3-item self-report adherence measure which showed good psychometric characteristics and good construct validity when compared with an electronic drug monitoring standard, for both HIV and non-HIV medications, and has been validated with culturally-diverse patient groups, including MSM (Fowler et al., 2014; Wilson et al., 2014; 2016). The items include: 1) In the last 30 days, on how many days did you miss at least one dose of any of PrEP (write in # of days) 2) In the last 30 days, how good a job did you do at taking your PrEP in the way you were supposed to? (6-point Likert) 3) In the last 30 days, how often did you take your PrEP in the way you were supposed to? (6-point Likert). Note: We will also examine self-report app adherence data. App adherence data can only be collected via the app as yes or no responses to pill reminders, and thus cannot serve as pre-intervention baseline. We will, however, compare app adherence data from weeks 1 and 12.

Consideration of Relevant Biological Variables: We will only include culturally-diverse young adult males who have sex with other males in our study as they are disproportionately represented among groups at increased risk for HIV. Moreover, males account for 95.3% of all PrEP users (Huang et al., 2018).

Mediating Variables: We propose four mediating variables: PrEP self-efficacy, intention to follow PrEP guidelines, PrEP knowledge and stress burden. To measure PrEP treatment self-efficacy, we will use the **Adherence Self-Efficacy Scale** (ASES) (Johnson et al., 2007). It is a 12-item scale of patients' confidence to carry out

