Perceived stress burden will be included as a potential mediating variable for two reasons: First, the intervention targets stress burden via supportive texts and an online community. Second, reductions in perceived stress can facilitate medication adherence (Stewart et al., 2005). Stress burden will be assessed using the 10-item **Perceived Stress Scale** (Cohen et al., 1983), which has been validated with a wide-range of patient and non-patient groups (e.g. Chiu et al., 2016; Perera et al., 2017). We will analyze psychometric properties and construct validity on the two new measures (intention to follow guidelines and PrEP knowledge) as a part of our Phase 2 analyses.

Moderating Variable. Length of time on PrEP (in months) will be included as a moderator as it seems possible that the greater the length of time on PrEP, the more likely a participant has developed personal strategies to support adherence or have supports (family members, friends, healthcare providers) in his social environment that help with adherence.

Demographic and Control Variables. T1 assessments will also gather a number of demographic indicators, including age, years of education, income and, as mentioned above, length of time on PrEP. Income will be coded categorically from 1 to 7 in relation to the federal poverty level: <100% (1), 100%-149% (2),

150%-199% (3), 200%-249% (4), 250%-299% (5),
300%-349% (6), 350%-399% (7), and $\geq 400\%$.

Randomization: Participants will be randomly assigned to intervention or control group via the randomizer function on Qualtrics software. **Sample size:** We will aim to recruit and gain consent from 110 participants (55 each for intervention and control arms). **Power analysis:** Based on our Phase 1 pretest results, an a priori power analysis for a multiple regression with 4 predictors of PrEP adherence was conducted to determine a sample size with a power of at least 90% with a two-sided alpha level of .05. The desired minimum sample size was 92 participants (Rosner, 2010). In the event of 20% attrition, we added 20% additional participants to the sample, and set 110 as the total sample size. Therefore, even if the study encounters diminished recruitment or greater post-recruitment attrition, it should still be possible to detect moderate effects.

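### Model 3 enters each participant's T1 and T2 records in ordinary linear regression with no allowance for within-person correlation, so the standard error of the interaction is wrong

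*SAP*

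**What the plan says.** SAP, Analysis plan, Hypothesis 1 names one method for the primary hypothesis: "We will employ multivariate linear regression to estimate the association between the intervention and PrEP adherence". Three models follow. Model 1 regresses 12-week adherence on arm. Model 2 adds age, education and income. Model 3 keeps those covariates and adds "the dichotomous treatment variable and the dichotomous intervention variable (before the intervention vs after) and their interaction". The SAP interprets the result as follows: "The coefficient of the interaction term will be the difference between the increase in intervention group and the increase in control group".

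The Measures section says of data collection "Both baseline (T1) and 12-week follow up (T2) data will be collected on the following key measures", and of the primary outcome "The primary outcome compares differences between (T1) and (T2) for the key measure of interest". The Data Analysis paragraph adds that "missing T2 data will be imputed to retain all participants in analyses", so all 110 planned participants (55 per arm) supply both time points.

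Data Analysis lists the methods as diagnostics, univariate statistics, bivariate tests and linear regression in SPSS. The diagnostics cover distribution shape, collinearity and unequal variance. Independence of residuals is not among them. No mixed model, GEE, participant effect, repeated-measures covariance, clustered or robust standard error, or change score appears in the SAP or the protocol.

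**The concern.** If the dependent variable were T2 adherence or the T1-T2 change, the before/after indicator would be constant and neither it nor its interaction with arm could be estimated. Model 3 therefore needs two rows per participant. Ordinary linear regression takes those rows as independent, but two reports of the same behaviour by the same person 12 weeks apart are very likely correlated. Age, education and income are measured once, at T1, so they remove only the part of that correlation that they explain. The planned diagnostics would not reveal what remains.

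The interaction is a within-person contrast, so ignoring a positive correlation overstates its standard error. What is at stake is a missed benefit on the declared primary outcome, with an interval that is too wide and a p-value that is too large. It is not a false claim of benefit. A negative correlation would reverse the direction.

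**Working it through.** **The plan's own figures.** The SAP gives no standard error or power for Model 3. Its power analysis (also Protocol 8.0) reports a minimum of 92 for a regression with 4 predictors, at 90% power and two-sided alpha .05. Four predictors fit Model 2 (arm plus three covariates), not Model 3. No numerical effect size is stated, so 92 cannot be reproduced. The step to 110 does reproduce: 92 × 1.2 = 110.4. Neither figure covers Model 3.

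**Inputs.** n = 55 per arm, two records each, two-sided alpha 0.05 (SAP). Assumed: outcome SD σ = 1 at both times and in both arms; T1-T2 correlation ρ = 0.3, 0.5 or 0.7 after the covariates; effect δ = 0.5 SD, because the SAP says only that the effect is moderate; complete data.

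**Standard error.** The interaction is (mean T2 - mean T1) in the intervention arm minus the same quantity in the control arm.

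- Ordinary regression treats the four cell means as independent, each with variance σ²/n: SE_OLS = σ√(4/n) = √(4/55) = 0.270 at every ρ.
- The mean change in one arm has variance 2σ²(1-ρ)/n, so SE_true = σ√(4(1-ρ)/n).
- The ratio is k = 1/√(1-ρ).

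The direction does not depend on equal variances. With SDs σ₁ and σ₂ at T1 and T2, the two variances are 2(σ₁²+σ₂²)/n and 2(σ₁²+σ₂²-2ρσ₁σ₂)/n. The first is larger whenever ρ > 0.

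**Size and power (normal approximation).** True size = 2[1-Φ(1.96k)]. Power as written = Φ((δ - 1.96·SE_OLS)/SE_true). Power with the correct SE = Φ(δ/SE_true - 1.96). For example, at ρ = 0.5 these powers are Φ((0.5 - 0.529)/0.191) = 44% and Φ(2.62 - 1.96) = 75%.

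| ρ | SE_OLS | SE_true | k | True size | Power as written | Power, correct SE |
|---|---|---|---|---|---|---|
| 0 | 0.270 | 0.270 | 1.00 | 5.0% | 46% | 46% |
| 0.3 | 0.270 | 0.226 | 1.20 | 1.9% | 45% | 60% |
| 0.5 | 0.270 | 0.191 | 1.41 | 0.56% | 44% | 75% |
| 0.7 | 0.270 | 0.148 | 1.83 | 0.03% | 42% | 92% |

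As ρ rises, the correct analysis gains power and the written one does not.

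**Simulation check.** 10,000 trials per setting, 55 per arm, three covariates. At ρ = 0.5 the interaction estimate had an empirical SD of 0.191, against a mean reported SE of 0.269 from stacked regression and 0.190 from a change-score regression. Null rejection was 0.55% stacked and 5.2% change score. At 0.5 SD, rejection was 43% and 74%.

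**With attrition.** At 20% loss, 110 × 0.8 = 88, or 44 per arm. At ρ = 0.5, SE_OLS = √(4/44) = 0.302 and SE_true = √(2/44) = 0.213. Power is Φ((0.5 - 0.592)/0.213) = 33% as written and Φ(2.35 - 1.96) = 65% corrected. The gap remains.

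**The case against.** The case on the other side has four parts.

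- **The SAP does not say that the rows are independent.** It gives model terms and an estimand but no error structure, and a paired fit would meet the same estimand. This is true. However, linear regression is the only regression method named, and nothing in either document would lead an analyst to anything else. If a paired analysis was meant, the text has to say so.
- **Models 1 and 2 also serve Hypothesis 1 and are unaffected.** They have one row per person, and under randomisation a 12-week comparison estimates the same effect in expectation. On the assumptions above, Model 1 has SE √(2/55) = 0.191 and power of about 75% at any ρ. That beats the corrected Model 3 at ρ = 0.3, equals it at 0.5 and falls below it at 0.7. This stands: the damage is confined to one of three models, and the SAP does not say which is primary. But Models 1 and 2 ignore T1 adherence, and only Model 3 matches the primary outcome as defined.
- **The error is conservative and the point estimate is sound.** This also stands for positive ρ. A p-value and interval that are wrong for the primary contrast still need correcting.
- **The magnitudes rest on assumed values of ρ and δ.** That is correct, and it is why a range is shown. Only at ρ = 0 does the problem vanish, and that is implausible for repeated reports from the same person.

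**Conclusion.** The concern holds. Followed as written, Model 3 gives an unbiased interaction estimate with an invalid standard error, interval and p-value. For T1-T2 correlations of 0.3 to 0.7 the standard error is 20% to 83% too large, and the nominal 5% test operates at about 1.9% down to 0.03%. For an assumed 0.5 SD effect with 55 per arm, 15 to 50 percentage points of power are lost (60 - 45 and 92 - 42). These figures assume equal variances and complete data. The power figures also depend on the assumed effect. The inflation factor and the true size depend only on ρ. Models 1 and 2 are not affected.

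**What to change.** Respecify Model 3 as a linear mixed model with a participant random intercept (SPSS MIXED), with fixed effects for arm, time, arm × time, age, education and income. Regressing the T2-T1 change on arm gives the same contrast, and with both time points complete essentially the same inference. Keeping the stacked model with standard errors clustered by participant is also acceptable and agrees closely in a sample of this size. Fit the chosen model in each imputed data set and pool the results. Delete the version without a within-person term.

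Two related choices should be settled in the same edit. First, state which Hypothesis 1 model is primary. Second, consider regressing T2 adherence on arm, T1 adherence and the three covariates. Its standard error is about σ√(2(1-ρ²)/n), which on the assumptions above gives power of 79%, 86% and 96% at ρ = 0.3, 0.5 and 0.7, higher than the change score at each value.

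The cost is a few lines of SAP text and a different procedure in the same software, with no new data and no change to trial conduct. It should be done before the outcome data are analysed.

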the mediation effect, the following three regressions will be conducted. First, we will set PrEP adherence as the dependent variable, demographic variables and dichotomous treatment variable and other independent variables as the independent variables. Second, we will set PrEP adherence as the dependent variable, and each of the four mediators as the independent variable. Third, we will set the dichotomous treatment variable as the dependent variable and each of the four mediators as the independent variables. The coefficients of the three regressions will show the mediation effects. Time on PrEP will be examined as a potential moderating variable, including the potential for moderated mediation in which mediators may become significant only at certain levels of the time since starting PrEP. Results will be interpreted via the standard interpretation of a sequence of regression models (Aneshensel, 2002; Baron & Kenny, 1986) to determine whether these variables mediate or partially mediate intervention effects, and the extent to which time on PrEP moderates these relationships.

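### Hypothesis 2 makes randomised treatment the outcome in its third regression, so no listed model directly estimates the app's effect on a mediator, and one undefined term decides whether mediation can be judged

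*SAP*

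**What the plan says.** The SAP, Analysis plan, states Hypothesis 2 as a causal chain: "The impact of intervention on the primary outcome will be mediated through key factors", namely higher self-efficacy, knowledge and intention to follow guidelines, and lower stress burden. It then lists three regressions.

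- Regression 1 has PrEP adherence as outcome, with "demographic variables and dichotomous treatment variable and other independent variables as the independent variables".
- Regression 2: "Second, we will set PrEP adherence as the dependent variable, and each of the four mediators as the independent variable". Treatment is not among its terms.
- Regression 3: "Third, we will set the dichotomous treatment variable as the dependent variable and each of the four mediators as the independent variables".

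The SAP adds: "The coefficients of the three regressions will show the mediation effects". A standard mediation framework is cited for interpretation, "to determine whether these variables mediate or partially mediate intervention effects". Time on PrEP is to be examined as a moderator, "including the potential for moderated mediation in which mediators may become significant only at certain levels". No other section of the SAP or protocol gives a regression with a mediator as outcome, or names an indirect effect or a confidence interval for one.

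**The concern.** A mediation analysis needs three quantities: the app's effect on the mediator (path a), the mediator's effect on adherence with arm held fixed (path b), and the app's remaining direct effect. The arm is assigned by a randomiser, so the mediators cannot cause it. A model with arm as outcome returns the change in the probability of being in the app arm per unit of the mediator, which is not an app effect on, for example, self-efficacy.

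Regression 2 leaves out treatment. If the app moves both the mediator and adherence, the two will be correlated even when the mediator does nothing. The model that would separate these is adherence on treatment and mediator together. Whether the plan contains it depends on the last, unlisted group of predictors in regression 1.

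At stake is whether Hypothesis 2 can be answered from the listed models, and whether a variable that the app moves but that does not affect adherence could be reported as a mediator.

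**Working it through.** **Inputs from the SAP.** 55 per arm (N=110), two-sided 0.05, linear regression, four mediators. The SAP gives no figure for Hypothesis 2, so there is none to reproduce.

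**Assumed.** Effects in residual-SD units, unit-variance normal errors, complete data on 110. Simulations of the significance rates used 20,000 trials per scenario.

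**Step 1. What Hypothesis 2 needs against what is listed.**

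| Needed | Model that gives it | In the SAP? |
|---|---|---|
| Path a | Mediator on treatment | No; regression 3 is the reverse |
| Path b | Adherence on treatment and mediator | Only if regression 1's unlisted group contains the mediators |
| Direct effect | Same model as path b | Same condition |
| Indirect effect with interval | a×b | Not named |

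**Step 2. Reversal with one mediator, no covariates.** Let M = aT + e, so Var(T) = 0.25 and Var(M) = 1 + 0.25a².

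- Slope of T on M = 0.25a/(1 + 0.25a²). At a = 0.5: 0.125/1.0625 = 0.1176.
- Rescaling by Var(M)/Var(T): 0.1176 × 1.0625/0.25 = 0.50, which is path a.
- The t statistic is the same in both directions (largest simulated difference about 8e-15).

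The test survives, and the effect is recoverable but not reported.

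**Step 3. Four mediators entered together.** With residual correlation matrix Σ, the regression 3 coefficients are 0.25Σ⁻¹a/(1 + 0.25a′Σ⁻¹a). With every a = 0.5 and common correlation ρ, each element of Σ⁻¹a is 0.5/(1 + 3ρ).

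| ρ | Element of Σ⁻¹a | a′Σ⁻¹a | Regression 3 coefficient | Detected per mediator (simulated) |
|---|---|---|---|---|
| 0 | 0.500 | 1.000 | 0.125/1.250 = 0.100 | 65% |
| 0.1 | 0.385 | 0.769 | 0.096/1.192 = 0.081 | 44% |
| 0.2 | 0.3125 | 0.625 | 0.078/1.156 = 0.068 | 30% |

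The path-a test (mediator on treatment) detects each in about 74%.

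**Step 4. Regression 2 without treatment.** Its slope is b + c′ × 0.25a/(1 + 0.25a²), where c′ is the direct effect. With b = 0 and a = c′:

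- 0.3: 0.0225/1.0225 = 0.02
- 0.5: 0.0625/1.0625 = 0.06
- 0.8: 0.16/1.16 = 0.14

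The true value is 0 in each case.

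**Step 5. The two readings of regression 1.** No true mediation; mediator and adherence are both shifted by d.

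- *Unlisted group excludes the mediators.* The rule assumed for this check is that all three regressions are significant.
- *Correct models.* Mediator on treatment, and the mediator term in adherence on treatment plus mediator, are both significant.
- *Unlisted group includes the mediators.* With one mediator, the same two tests are available and the rates equal those of the correct models.

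| d (SD) | 0.3 | 0.4 | 0.5 | 0.6 | 0.8 |
|---|---|---|---|---|---|
| Mediators excluded | 0.9% | 3.1% | 6.9% | 12.6% | 30.2% |
| Correct models | 1.8% | 2.8% | 3.7% | 4.5% | 4.9% |

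**The case against.** The strongest defence is that the stated aim and the cited framework make sense only if regression 1 contains the mediators. Regression 3, run one mediator at a time, is then a valid association test, and false positives are not inflated. This is a fair reading, and on it the defect is mainly one of reporting. But the citation governs interpretation and does not change the listed equations, and the wording of regression 3 does not settle joint or separate entry. The false-positive rule in Step 5 is also not the SAP's, which states none.

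Some stronger inferences are tempting, but the documents do not support them:

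- *That all of regression 1 is undefined.* Treatment is clear, and Hypothesis 1 names the demographic covariates as age, education and income. Only the last group is unlisted.
- *That the indirect effect can be split by mediator only if they enter one at a time.* Without covariates, rescaled one-at-a-time slopes from regression 3 multiplied by joint path-b coefficients sum exactly to total minus direct effect.
- *That differing covariates spoil total minus direct.* Time on PrEP is listed among the T1 demographic indicators but is not in the second Hypothesis 1 model. Under randomisation this costs an exact identity and does not bias the linear total effect.
- *That joint entry would credit an unmoved mediator.* With three mediators shifted 0.5 SD and one unmoved, the unmoved one is flagged in 5.2%, 9.4% and 18.6% of trials at ρ = 0, 0.1 and 0.2. But 2.7, 8.9 and 18.5 points of these have the wrong sign. Flags in the direction Hypothesis 2 states are 2.5%, 0.5% and 0.1%. The loss of power in Step 3 does stand.
- *That the r>0.4 selection rule would remove baseline values from the mediation models.* The rule sits under Hypothesis 1 and concerns similar variables. The SAP does not apply it to T1 and T2 scores of one scale.

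**Conclusion.** The concern holds for Hypothesis 2. Regression 3 is wrong as written, regression 2 lacks treatment, and one undefined term decides whether any model can separate mediated from direct effects. If that term includes the mediators, path b and the direct effect are available, there is no false-positive inflation, and what is missing is a reported indirect effect with its interval. If it does not, full or partial mediation cannot be determined. Crediting a non-mediator is then material only for larger effects: there is no excess of note at 0.3 to 0.4 SD, about 7% against 4% at 0.5 SD, and 30% against 5% at 0.8 SD.

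The equation-level defect needs no assumed effect size; every percentage does, and also rests on normal errors and complete data. A reader might infer that the trial's main comparison or sample size is compromised. Neither depends on these regressions, so this should be fixed but does not threaten Hypothesis 1.

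**What to change.** State the terms of regression 1 and replace regressions 2 and 3. For each mediator:

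- (a) Regress the T2 mediator on treatment, T1 mediator, age, education and income.
- (b) Regress T2 adherence on treatment, T2 mediator, T1 mediator, T1 adherence, age, education and income.

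If total = direct + indirect is to hold exactly, add T1 adherence to (a) and fit the total effect with the same covariates.

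Report a×b with a bootstrap 95% confidence interval and the direct effect from (b). Say how the bootstrap is combined with the planned multiple imputation, for example by bootstrapping within each imputed data set and pooling. For the planned moderated mediation, add time on PrEP and its interaction with treatment to (a), and time on PrEP and its interactions with treatment and mediator to (b). A joint four-mediator version of (b) can be an optional sensitivity analysis.

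The cost is SAP wording and modest extra analysis. No new data are needed: mediators and adherence are collected at T1 and T2, and the covariates and time on PrEP at T1. The repair does not remove the usual limit that the mediators are not randomised, which the report should state.

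### Hypothesis 2 has no estimate or interval for the indirect effect, and its full-or-partial mediation label is biased toward full at 88 to 110 participants

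*SAP*

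**What the plan says.** The SAP's Analysis plan, Hypothesis 2, names four mediators: PrEP self-efficacy, PrEP knowledge, intention to follow guidelines, and stress burden. It lists three regressions and states: "The coefficients of the three regressions will show the mediation effects". The results are then read as a sequence of regression models, with two methodological sources cited, "to determine whether these variables mediate or partially mediate intervention effects".

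The SAP does not define an indirect effect, plan an interval for one, define the two labels, write out a p-value rule, or mention multiplicity over the four mediators.

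The sample size rests on "an a priori power analysis for a multiple regression with 4 predictors of PrEP adherence", with "power of at least 90% with a two-sided alpha level of .05". No power is given for mediation, and the only effect size is verbal: "it should still be possible to detect moderate effects".

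**The concern.** A mediation claim is a claim about one quantity: the arm's effect on the mediator multiplied by the mediator's effect on adherence, holding arm fixed. The SAP never estimates that product, so Hypothesis 2 would end in a verbal label with no size and no stated uncertainty.

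The label has its own problem. On the usual causal-steps reading, mediation is full when the direct effect is no longer significant and partial when it still is. Failure to reach significance is then read as absence of effect. In about 100 participants a real direct effect of moderate size often misses p<0.05, so the label leans toward full. At stake is the trial's account of how the app works: a report could say that the app acts wholly through, say, self-efficacy when most of its effect takes another route.

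**Working it through.** **The plan's own figure.** "The desired minimum sample size was 92 participants", then "In the event of 20% attrition, we added 20% additional participants to the sample, and set 110 as the total sample size", with "55 each for intervention and control arms". 92 × 1.2 = 110.4, which gives 110. After 20% loss, 110 × 0.8 = 88 remain. The 92 itself cannot be reproduced, because no numerical effect size is given. Imputation keeps the nominal n at 110, but 88 may be all that have observed follow-up, so both sizes are used.

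**Assumed inputs (not in the documents).** Arm to mediator a = 0.5 SD; mediator coefficient b = 0.4; direct effect c' = 0.3 SD; one mediator per model, normal errors, complete data, correctly specified models:

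- M = 0.5·arm + e₁
- Y = 0.3·arm + 0.4·M + √(1 − 0.16)·e₂

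Indirect effect = 0.5 × 0.4 = 0.20. Total = 0.30 + 0.20 = 0.50. Share mediated = 0.20/0.50 = 40%, so 60% is direct and partial is the true label.

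**Hand check of the label.** The standard error of the direct effect is about 2·√0.84·√(1 + a²/4)/√n = 2 × 0.917 × 1.031/√n = 1.89/√n.

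- n=110: 0.180. z = 0.3/0.180 = 1.67. Chance of non-significance ≈ Φ(1.96 − 1.67) ≈ 62%.
- n=88: 0.201. z = 1.49. Chance of non-significance ≈ Φ(0.47) ≈ 68%.

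**Simulation of the same scenario** (4,000 trials per setting; repeat runs agreed within about two points). Mediation is claimed when a and b (given arm) both have p<0.05, with or without also requiring p<0.05 for the total effect. Full means a direct-effect p of 0.05 or more. The interval is the 95% Monte Carlo interval for a·b.

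| | n=110 | n=88 |
|---|---|---|
| Wrongly full among claims, total effect required | 54% | 59% |
| Wrongly full among claims, total effect not required | 63% | 70% |
| Power, total effect required | 59% | 46% |
| Power, total effect not required | 73% | 62% |
| Power, 95% interval for a·b | 74% | 63% |
| Power, interval at Holm's strictest step (98.75%) | 54% | 41% |

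**Other assumed truths at n=92, total effect required.** Share of claims wrongly called full:

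- half mediated: 55–72%
- two thirds to three quarters mediated: 81–90%
- 25–29% mediated: 22–46%
- one third mediated with a very large direct effect (total 1.07 SD): 6%

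When mediation is complete, full is the correct label in 88–98% of claims.

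**Size of the power loss if a total effect is required (n=92).** At a total effect of d=0.676, which a plain two-arm comparison of 92 detects with 90% power, and with half mediated, power is 81–86% against 89–95% for the interval. With complete mediation and a small total effect (a=0.8, b=0.5, d=0.36) it is 39% against 96%.

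**Four mediators, none affecting adherence, n=110.** The chance of at least one false claim is about 14% (total effect required) to 18% (not required) when the app moves all four by 0.8 SD, and 11% to 14% at 0.5 SD. It is about 1% when the mediators are inert on both paths.

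**The case against.** The strongest reply is that much of the rule is inferred. The SAP writes no p-value rule, does not make a significant total effect a precondition, and leaves the labels to sources not reproduced in it. That stands, and it limits three stronger conclusions that a reader might draw.

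- **That Hypothesis 2 loses power.** The loss comes almost entirely from requiring a significant total effect. Without that requirement the sequence has practically the same power as the interval (73% against 74% at n=110). The cited approach implies the requirement, but the SAP does not state it.
- **That the label is mostly noise.** It is usually right under complete mediation and less often wrong with a large direct effect. It is biased in one direction, not random.
- **That four mediators carry an 18.5% risk of a false finding (1 − 0.95⁴).** That treats mediation as one 5% test per mediator. A claim needs at least two tests to pass, so inert mediators give about 1%. The risk approaches that figure only when the app strongly moves all four and none matters for adherence.

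It is also fair to say that Hypothesis 2 is explanatory and does not touch the primary comparison, and that the regressions themselves need repair first. Neither point rescues the label. Its bias does not depend on the unwritten total-effect requirement (without it, the error rises), and it would remain after the regressions are corrected.

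**Conclusion.** The concern holds in a limited form. The SAP specifies no indirect effect and no interval, and its full-or-partial label, read in the usual way, is biased toward full and unreliable at 88 to 110 participants. In the 40%-mediated scenario the label is wrong in 54–59% of claims, or 63–70% if no significant total effect is required. The power loss (74% to 59% at n=110, 63% to 46% at n=88) is conditional on a requirement that the SAP should either state or disown.

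All mediation figures rest on assumed paths, one mediator per model, normal errors and complete data. The documents give no path values, so the direction of the bias is firmer than any single percentage.

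**What to change.** 1. **Respecify the models first.** As written, the second regression omits arm and the third makes arm the dependent variable. Use mediator on arm, and adherence on arm plus mediator. An interval alone does not cure this: with b=0, a=0.8 and a direct effect of 0.7 at n=92, leaving arm out of the second model gives a false mediation claim in 21% of trials, against 5% with arm included.
2. **Estimate the indirect effect** for each mediator as the arm effect on the mediator times the mediator coefficient in the model that contains arm. Give it a 95% Monte Carlo or bootstrap interval, and state how this is combined with the multiple imputation.
3. **Conclude from that interval**, and say that a significant total effect is not required.
4. **Delete the full/partial label** and report the direct effect with its own interval.
5. **Decide on multiplicity openly.** Adjustment over the four mediators is optional. At Holm's strictest step, power in the scenario above falls from 74% to 54% (n=110) and from 63% to 41% (n=88), below even the sequence with a total-effect requirement; later Holm steps are milder. Without adjustment, state that the four mediator results are unadjusted and explanatory.

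The cost is SAP wording and a short piece of code. No new data are needed.
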